9.3. Statistical Analyses

The statistical analysis plan (SAP) will be finalized prior to database lock and it will include a more technical and detailed description of the statistical analyses described in this section. This section is a summary of the planned statistical analyses of the most important endpoints including primary and key secondary endpoints.

The standard summary statistics for continuous variables are sample size (n), mean, standard deviation, median, minimum and maximum. The standard summary statistics for categorical variables are frequencies and percentages. Time to event variables will be summarized using the Kaplan-Meier method. Where confidence limits are appropriate, the confidence level will be 95% (two-sided), unless otherwise stated. The only test of statistical significance will be performed according to the pre-defined analysis of the Simon two-stage optimal design.

Individual data (including relevant derived variables) will be presented by parameter in listings. Results of statistical analyses, descriptive summary statistics and supportive listings will also be presented.

Baseline values are defined as the last valid value prior to IP administration. Baseline safety data will be presented along with subsequent safety values assessed during or after drug administration.

Detailed methodology for summary and statistical analyses of the data collected in this study will be documented in a statistical analysis plan (SAP), which will be maintained by the Sponsor. This document may modify the plans outlined in the protocol; however, any major modifications will also be reflected in a protocol amendment.

Statistical analyses will be performed using SAS® v9.4 or higher (SAS Institute, Cary NC, USA).

9.3.1. Subject Disposition

The number and percentage of subjects who are enrolled, treated, discontinued from IP, and participating in follow-up will be presented for the Safety analysis and the Efficacy Evaluable population. A summary of reasons for discontinuation from treatment and withdrawal from the study will be provided. The number of subjects included in each analysis set will be summarized and the reasons for excluding subjects from each population will be listed.

9.3.2. Demographic and Baseline Characteristics

Demographic characteristics including age, gender, race, and ethnicity will be presented in the form of tabular summary statistics for all subjects in all of the above populations. Other subject baseline characteristics including weight, height, body mass index (BMI), initial stage of disease, and performance status will be presented similarly.

9.3.3. Efficacy

9.3.3.1. Definitions of Efficacy Endpoints

Primary: ORR, defined as the proportion of subjects who have a best overall response (BOR) of CR or PR as determined using RECIST v1.1. BOR is defined as the best response recorded between the date of first dose of IP and the date of subsequent anti-cancer therapy. A BOR of CR or PR requires confirmation of the assessment no earlier than 4 weeks later.

Other efficacy endpoints are as follows:

- Progression free is defined as the interval from the start of study treatment to the earlier of the first documentation of disease progression or death from any cause.
- Clinical Benefit Response is defined as SD+PR+CR.
- DOR, defined as the interval from the first documentation of CR or PR to the earlier of the first documentation of disease progression (per RECIST v1.1) or death from any cause.
- OS, defined as the time from the date of start of treatment to the date of death from any cause. Subjects who are lost to follow-up and those not known to have died by the cut-off date for analysis will be censored on the date the subject was last known alive, or the data cut-off date, whichever is earlier.

9.3.3.2. Analysis of Efficacy Endpoints

For primary and secondary endpoints refer to Section 1.2.

The primary efficacy endpoint is the ORR based on the proportion of subjects with an overall response of either CR or PR. Disease response will be assessed using RECIST v1.1. Primary efficacy analysis will be performed on the Efficacy Evaluable population.

Secondary endpoints include CBR, DOR, PFS, PFS at 6 months, and OS. Secondary efficacy analysis will be performed on the Efficacy Evaluable population and Per Protocol population.

Efficacy endpoints will also be analyzed for each of the sub-populations: TNBC subjects as well as non-TNBC subjects.

9.3.4. Safety and Tolerability Analysis

All safety analyses will be made on the Safety Analysis population.

The safety assessment will be based on the frequency of AEs, the incidence of clinically significant abnormalities of laboratory values, concomitant medication use, vital signs, pain assessment and physical examination data.

Adverse events: The AE verbatim descriptions (investigator terms from the eCRF) will be classified into standardized medical terminology using the Medical Dictionary for Regulatory Activities (MedDRA). AEs will be considered treatment-emergent if they start on or any time after the first dose of IP until 30 days after the last dose of IP. The incidence of treatment-emergent AEs will be summarized overall, by system organ class and preferred terms, and by severity grade and relationship to IP. SAEs and AEs leading to discontinuation will also be tabulated.

Other safety data: These data will be summarized by presenting the proportions of subjects with clinically significant abnormalities or by changes from baseline values. Laboratory parameters will be categorized according to CTCAE v5.0 grade and shifts from baseline CTCAE grade to worst postbaseline grade will be summarized using shift tables. Percentages will be based on the number of subjects with baseline and at least 1 post baseline assessment. Laboratory data will be listed, and abnormal results will be flagged.

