3. OBJECTIVES AND ENDPOINTS

Objectives	Endpoints
Primary 
 To evaluate the efficacy of AL101 monotherapy in subjects with Notch-activated recurrent or metastatic TNBC 	
 Proportion of subjects who demonstrate an overall response rate (ORR), defined as PR + CR as assessed by investigator based on Response Evaluation Criteria in Solid Tumors (RECIST) v1.1
Secondary 
 Efficacy - Secondary 	
 Clinical benefit response rate (CBR) defined as CR +PR + stable disease (SD) by investigator review based on RECIST v1.1 Duration of response (DOR) by investigator review based on RECIST v1.1 Progression free survival (PFS) Proportion of subjects who have PFS at 6 months Overall survival (OS) Quality of life (QoL) as determined by European Organization for Research and Treatment of Cancer Quality of Life Questionnaire 30 questions (EORTC QLQ-C30) and Breast Cancer 45 questions (EORTC QLQ-BR45)

 To evaluate the safety and tolerability of AL101 monotherapy in subjects with recurrent or metastatic TNBC 	
 Frequency, duration and severity of treatment-emergent adverse events (TEAEs) and serious adverse events (SAEs) Incidence of clinically significant abnormalities in laboratory parameters, electrocardiograms (ECGs), vital signs and physical examination

Objectives	Endpoints
Exploratory 
 • To characterize biomarkers as a measure of response to AL101 monotherapy, and overall prognosis • To establish correlation between positive Notch intracellular domain (NICD) immunohistochemistry (IHC) stain and Notch activating mutations • To establish the correlation between mutations in Notch and associated genes and response or resistance to investigational product 	Endpoints 
 • Change in quantity of circulating tumor cells (CTCs), and other biomarkers in CTCs • Predictive biomarkers of response or resistance to the investigational product will be explored: 
 – IHC: Tumor specimens will be stained for NICD and other potential biomarkers. – NGS: Mutational analysis of tumor tissue samples, and potentially cfDNA and CTCs. – Gene expression analysis in tumor tissue samples.

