8.3. Adverse Events and Serious Adverse Events

Progression of the cancer under study is not considered an adverse event.

The definitions of an AE and SAE can be found in Appendix 3 (Section 10.3). The definition of AESI can be found in Section 8.3.5.

AEs will be reported by the subject (or, when appropriate, by a caregiver, surrogate, or the subject's legally authorized representative).

The investigator and any qualified designees are responsible for detecting, documenting, and recording events that meet the definition of an AE, SAE, or AESI. Investigators remain responsible for following up AE, SAEs and other reportable safety events for outcome.

8.3.1. Time Period and Frequency for Collecting AE, SAE and Other Reportable Safety Event Information

All AEs, SAEs and other reportable safety events that occur after the consent form is signed but before IP administration must be reported by the investigator if the event cause the subject to be excluded from the study, or is the result of a protocol-specified intervention, including but not limited to washout or discontinuation of usual therapy, diet, or a procedure.

Table 7 below summarizes the different reporting timelines for AEs, SAEs, SUSAR, AESIs and pregnancy.

Table 7 Adverse Event Reporting Timelines to the Sponsor

Type of Event	AE	SAE / SUSAR	AESI related to IP	Pregnancy
Reporting period	From consent until 30 days after last dose of IP	From consent until 30 days after the last IP dose, and any time after that window if the SAEs are believed to be related to AL101	From consent until 30 days after the last dose of IP, or the initiation of a new anti-cancer therapy	From consent until 120 days after last dose of IP
Reporting Timelines to the Sponsor	Entered into the clinical database on an ongoing basis	Within 24 hours	Within 24 hours	Within 24 hours
Reporting Method	AE eCRF	AE eCRF	AE eCRF	Pregnancy form in eCRF

Abbreviation: Adverse event (AE), adverse events of special interest (AESI), Serious adverse event (SAE), serious unexpected suspected adverse reaction (SUSAR)

Medical occurrences that begin before the start of IP but after obtaining informed consent will be recorded on the Medical History/Current Medical Conditions section of the eCRF not the AE section.

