- The investigator may change his/her opinion of causality in light of follow-up information and send a SAE follow-up report with the updated causality assessment.
- The causality assessment is one of the criteria used when determining regulatory reporting requirements.

Follow-up of AEs and SAEs

- The investigator is obligated to perform or arrange for the conduct of supplemental measurements and/or evaluations as medically indicated or as requested by the Sponsor to elucidate the nature and/or causality of the AE or SAE as fully as possible. This may include additional laboratory tests or investigations, histopathological examinations, or consultation with other health care professionals.
- If a subject dies during participation in the study or during a recognized follow-up period, the investigator will provide the Sponsor with a copy of any post-mortem findings including histopathology if an autopsy is performed.
- New or updated information will be recorded in the originally completed eCRF.
- The investigator will submit any updated SAE data to the Sponsor within 24 hours of receipt of the information.

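### TEAE status rests on start date alone and Section 8.3.1 gives conflicting recording rules for pre-dose events, so a screening event that worsens on AL101 can count as a TEAE at one site and not at another

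*Combined protocol and SAP*

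**What the plan says.** Section 9.3.4 states that "AEs will be considered treatment-emergent if they start on or any time after the first dose of IP", with the window closing 30 days after the last dose. Start date is the only criterion. Under Section 3, the secondary safety endpoint covers how often TEAEs and SAEs occur, how long they last and how severe they are.

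Section 8.3.1 addresses events between consent and first dose in three places:

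- The opening paragraph says that they "must be reported by the investigator if the event cause the subject to be excluded from the study", or if they result from a protocol-specified intervention such as a procedure.
- Table 7 gives the AE reporting period as "From consent until 30 days after last dose of IP", on the AE eCRF and without conditions.
- The text after Table 7 says that occurrences in this window "will be recorded on the Medical History/Current Medical Conditions section of the eCRF not the AE section".

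Two parts of Appendix 3 bear on what happens when such an event worsens. Section 10.3.1 treats exacerbation of a chronic or intermittent pre-existing condition as an AE, and likewise clinically significant test results that worsen from baseline. The follow-up part of Section 10.3.4 says "New or updated information will be recorded in the originally completed eCRF".

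**The concern.** In a single-arm study the TEAE tables are the main description of tolerability. A definition based on start date alone works only if every worsening on treatment gets its own record with its own start date. The protocol does not require that, and its two clearly opposed instructions for the pre-dose window lead to different records for the same clinical course.

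Any misclassification runs one way: the events at risk of dropping out are those that the drug may have aggravated. The start date also feeds the duration component of the endpoint, so the choice of record affects more than the count.

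**Working it through.** No figure in the plan needs reproducing, and no arithmetic applies. The check is to follow one event through the text.

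**Inputs.** TEAE rule: Section 9.3.4. Pre-dose recording: the opening paragraph, Table 7 and closing text of Section 8.3.1. AE definition: Section 10.3.1. Updating of records: Section 10.3.4.

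**Case.** A subject develops Grade 1 nausea after consent and before the first infusion. It reaches Grade 3 on AL101.

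| Instruction the site follows | Pre-dose record | Record of the worsening | TEAE under 9.3.4? |
|---|---|---|---|
| Closing text of 8.3.1 | Medical History | New AE under 10.3.1, dated after first dose | Yes |
| Closing text of 8.3.1 | Medical History | None, if the site does not regard the condition as chronic or intermittent | No |
| Table 7 | AE eCRF, pre-dose start | Original record updated under 10.3.4, start date unchanged | No |
| Table 7 | AE eCRF, pre-dose start | Separate new AE under 10.3.1 | Yes |
| Opening paragraph (condition not met) | None | New AE, if entered | Yes, if entered |

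**Reading the table.**

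1. Table 7 and the closing text cannot both be followed for an ordinary pre-dose AE. One puts it on the AE eCRF and the other excludes it from there. The Schedule of Activities also marks AE collection at screening, which makes the Table 7 reading a natural one.
2. No section says whether worsening opens a new record. Section 10.3.1 makes many exacerbations AEs in their own right, and Section 10.3.4 sends updates to the existing form. A site can cite either.
3. The first and third rows are both defensible readings and classify the same event differently.

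**Scope.** The conflict concerns events that begin between consent and first dose; screening lasts up to 28 days. Laboratory worsening is mostly protected. Section 8.2.6 asks for abnormal values that lead to a dose change, an intervention or added medication to be recorded as AEs, and Section 9.3.4 plans CTCAE shift tables from baseline to worst grade. Those tables cover laboratory parameters only, so nausea, fatigue and neuropathy have no such second route.

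**The case against.** The strongest reply is that the loss is possible but not certain. Section 10.3.4 does not say that a grade increase keeps the old start date; the sentence sits among general follow-up duties. Nothing in Section 10.3.1 confines the exacerbation rule to conditions held in Medical History, so a Table 7 site could properly open a new AE. The opening and closing texts of Section 8.3.1 can also be read together: reportable pre-dose events are reported and the rest go to Medical History. Finally, Section 9.3 leaves detail to a statistical analysis plan to be finalised before database lock, where a worsening clause could be added.

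Most of this stands, and it is why the point is that an event *can* drop out, not that it will. It does not close the gap. The Table 7 conflict remains on any reading, and an analysis plan cannot recover a date of worsening that sites were never told to record.

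A reader might infer three stronger things that the documents do not support:

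- *That serious screening events escape reporting.* The opening paragraph of Section 8.3.1 requires reporting of events caused by a protocol procedure. The same section, just after the closing text, requires all SAEs to reach the sponsor within 24 hours, and Section 5.5 collects SAEs even for screen failures.
- *That Grade 3 diarrhea or transaminase elevations would go missing.* Exclusion criterion 4 largely removes ongoing diarrhea at entry, and an episode after a resolved one is a new event. Transaminase worsening is covered by Section 8.2.6 and the shift tables.
- *That a number of lost subjects can be stated.* The documents give neither the frequency of screening-onset events nor the chance that one worsens.

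**Conclusion.** The point holds as an inconsistency of classification. A non-laboratory event that starts in screening and worsens on AL101 can be counted as a TEAE or not, depending on which recording instruction the site followed. This touches a secondary safety endpoint, and its size cannot be computed from the documents. It rests on two assumptions: that some subjects have such events, and that some sites follow Table 7 and update the original record. Both are plausible, and neither is quantified.

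ORR is unaffected. The lead-in safety criteria are also unaffected, because they count subjects who experience Grade 3 or 4 events and do not use the TEAE definition. The correction is worth making because it is cheap and the possible error hides drug-aggravated events.

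**What to change.** - **Section 9.3.4:** define a TEAE as an AE that starts, or increases in CTCAE grade, on or after the first dose and up to 30 days after the last dose.
- **Section 8.3.1 and Table 7:** keep one rule. SAEs, and AEs due to protocol procedures, go on the AE eCRF from consent. Other pre-dose events go to Medical History with their grade. The opening paragraph's condition on events that lead to exclusion can stay, since those subjects are not dosed and do not enter the TEAE count.
- **Section 10.3.4:** state that worsening after the first dose is a new AE record, dated at the worsening.

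The first change needs the third: without a dated record of the worsening, the wider definition cannot be applied consistently. If sites have already entered screening AEs under Table 7, those records need a query for the date and grade of any worsening.

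The cost is wording in these sections and an eCRF completion note. Treatment, visits and sample size do not change. The downside is that TEAE counts may be slightly higher.

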9.4. Interim Analyses

Because a Simon two-stage optimal design will be employed, ORR will be assessed during Stage 1 for subjects who have received IP for at least 2 cycles (8 weeks) and no more than 8 cycles (8 months). While the data on Stage 1 is maturing, Stage 2 will continue enrolling an additional 41 subjects for a total of 67 subjects, unless an unexpected safety signal emerges that in the judgement of the DMC requires analysis and/or poses a serious threat to the well-being of the subject.

The Statistical Analysis Plan will describe the planned analyses in greater detail.

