If acceptable genotyping results are not available, testing of a sample collected from a locally advanced or metastatic lesion must be conducted during pre-screening using a commercially available NGS assay, LDT or other validated investigational use only (IUO) clinical trial assay capable of detecting genetic alterations in the *NOTCH 1/2/3/4* genes. For this purpose, tumor biopsy from within the last 2 years or fresh biopsy will be needed.

After signing an informed consent, all subjects will then undergo screening assessments to determine study eligibility over a 28-day Screening period. Eligibility criteria for study entry will be assessed locally by the investigator; radiographic scans at screening and from the prior 12 months will be collected and held for possible future retrospective independent evaluation. Tumor tissue will need to be provided during the Screening period for confirmatory study-specific testing.

Starting on Cycle 1, Day 1, eligible subjects will be treated with IP intravenously (IV) QW, on Days 1, 8, 15 and 22 of each 28-day cycle. Treatment will continue until the occurrence of unequivocal radiographic disease progression per RECIST v1.1 as assessed by the investigator, or clear clinical progression as assessed by the investigator, or unacceptable toxicity, or other reasons for discontinuation.

All subjects will receive premedication with H1- and H2-blockers per institution guideline (refer to Section 6.6.1) and steroids as prophylaxis (refer to Section 6.6.2). Toxicity post-AL101 administration will be managed as specified in Section 6.4.

During the Treatment period, subjects will undergo radiographic assessments every 8 weeks (± 3 days) for review by the investigator. Radiographic scans will also be collected and held for possible future retrospective independent evaluation. Other assessments will be done as specified in the Schedule of Activities (Table 1). A repeat of tumor imaging will be required for the purposes of confirmation of response (i.e., partial response, and/or complete response). The confirmation scan should be no earlier than 4 weeks following the first indication of response.

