9. STATISTICAL CONSIDERATIONS

9.1. Statistical Hypothesis and Sample Size Determination

The study will utilize the Simon two-stage optimal design (Figure 1 and Table 8) and will include up to 67 to 73 subjects, depending on IP dose evaluated in Stage 1 and Stage 2 as follows:

- if the AL101 dose is 6 mg QW throughout the study, there will be up to 67 subjects evaluated, including the 6 subjects in the lead-in cohort for the Stage 1 evaluation.
- if AL101 4 mg is evaluated in Stage 1 and Stage 2, there will be up to 73 enrolled subjects consisting of up to 67 subjects at AL101 4 mg and 6 subjects in the lead-in cohort of AL101 6 mg. Note, the lead-in cohort will not be included in the Stage 1 evaluation.

In both scenarios there will be up to 26 evaluable subjects in Stage 1, and 41 additional evaluable subjects in Stage 2 provided at least 4 subjects (out of 26) responded in Stage 1.

While the data on Stage 1 is maturing, Stage 2 will continue enrolling an additional 41 subjects, unless an unexpected safety signal emerges that in the judgement of the DMC requires analysis and/or poses a serious threat to the well-being of the subject. This decision will be made in agreement with the Sponsor.

If no more than 3 subjects respond in Stage 1, the study will be stopped for futility. If 4 or more subjects respond, Stage 1 will be considered positive. For the entire study (Stages 1 and 2), the null hypothesis will be rejected if 15 or more responses are observed in 67 subjects. Only the Efficacy Evaluable set of subjects will be counted toward this analysis. This design has 80% power at the 5% type I error level to detect a desirable success rate of 23% against the null hypothesis of an unacceptable success rate of 11%. The success rate parameters for the two-stage design are aligned with recent published experience of clinical studies (Twelves, 2014). If at the end of Stage 1, there are 4 responses in the Notch-activated TNBC subjects, the study will continue to Stage 2.

Table 8 Sample Size Hypothesis

Total	Look1	Futility Boundary		Attained	Attained	Probability of	Expected
							Sample Size
(n)	(n_1)	Look1	Look2	Alpha	Power	Early	H0 (EN0)
		(r_1)	(r_2)			Stopping	
67	26	3	11	0.049	0.807	0.681	39.1

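### The Stage 1 response read is allowed from 8 weeks on treatment, but on scheduled scans a confirmed response takes about 12 weeks, and nothing protects pending responses from the futility rule

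*Combined protocol and SAP*

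**What the plan says.** Four parts of the protocol bear on this point.

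- **Timing of the Stage 1 read (Section 9.4).** "ORR will be assessed during Stage 1 for subjects who have received IP for at least 2 cycles (8 weeks"; the sentence then adds an upper limit of 8 cycles. This is the only timing condition given for the read. Sections 9.1 and 9.4 also say that Stage 2 keeps enrolling while Stage 1 data mature.
- **Definition of response (Section 9.3.3.1).** "A BOR of CR or PR requires confirmation of the assessment no earlier than 4 weeks later". Sections 4.1 and 8.1.1 also require the confirmation scan.
- **Scan schedule (Section 4.1).** On treatment, "subjects will undergo radiographic assessments every 8 weeks", with a window of 3 days either side.
- **Stop rule (Section 9.1).** "If no more than 3 subjects respond in Stage 1, the study will be stopped for futility". The rule counts the Efficacy Evaluable set. Under Section 9.2 a subject with measurable disease at baseline, dosed at the selected dose, enters that set with one post-baseline tumor assessment.

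The documents do not say whether the Stage 1 count uses confirmed responses, when the Stage 1 data are cut, or what happens to a first PR or CR whose confirmation scan is still to come.

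**The concern.** The minimum exposure for the read is shorter than the time the endpoint needs. A subject at 8 weeks has had one scheduled scan. That is enough to be evaluable and to be one of the 26, but not enough to have a confirmed response on the planned schedule. Table 8 is calculated as if each of the 26 had a full chance to respond. If the look is taken with some subjects near the minimum and the ORR definition is applied as written, real responses are missing from the count. The bar of 4 responses is then harder to reach than the design assumes, and the decision it drives is to stop the study.

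**Working it through.** **Inputs.** Section 9.1 gives the response rates ("detect a desirable success rate of 23% against the null hypothesis of an unacceptable success rate of 11" percent), the error rates ("This design has 80% power at the 5% type I error level") and the stage sizes ("there will be up to 26 evaluable subjects in Stage 1, and 41 additional evaluable subjects in Stage 2"). The Table 8 row reads "67 26 3 11 0.049 0.807 0.681 39.1": total 67, Stage 1 26, boundaries 3 and 11, alpha, power, probability of early stopping, expected sample size.

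**Step 1: earliest confirmed response on scheduled scans.** First scan at week 8 ± 3 days, that is day 53 to 59. Adding 4 weeks (28 days) gives day 81 to 87, or 11.6 to 12.4 weeks. A response first seen at the week 16 scan is confirmed at about week 20.

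**Step 2: reproduce the plan's design.** Let X1 ~ Bin(26, p) and X2 ~ Bin(41, p). Stop if X1 ≤ 3; otherwise reject the null if X1 + X2 > 11.

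- Early stopping at p = 0.11: P(X1 ≤ 3) = 0.681.
- Expected sample size at p = 0.11: 26 + (1 − 0.6807) × 41 = 39.1.
- Alpha = 0.049; power at p = 0.23 = 0.807.
- False futility stop at p = 0.23: P(X1 ≤ 3) = 0.0011 + 0.0087 + 0.0324 + 0.0775 = 0.120.

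All four Table 8 figures are reproduced.

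**Step 3: let k of the 26 be immature at the look.** Suppose no response among these k is visible yet. The Stage 1 count then comes from 26 − k subjects, so

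false stop = P(Bin(26 − k, 0.23) ≤ 3).

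If the study continues, all true responses count at the end, including those of the k subjects, so

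power = Σ over a ≥ 4 and b of P(Bin(26 − k, 0.23) = a) × P(Bin(k, 0.23) = b) × P(X2 ≥ 12 − a − b).

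Alpha uses the same sum with 0.11.

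| k immature | False stop at 23% | Power | Alpha |
|---|---|---|---|
| 0 | 12.0% | 0.807 | 0.049 |
| 1 | 14.0% | 0.791 | 0.047 |
| 2 | 16.4% | 0.773 | 0.045 |
| 4 | 22.0% | 0.727 | 0.040 |
| 6 | 29.2% | 0.666 | 0.035 |

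If each immature response has a one-half chance of being visible at the look, k = 4 gives a false stop of 16.5% and power of 0.772.

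**What k means.** If the look is taken when the last Stage 1 subject reaches 8 weeks, k is roughly the number first dosed in the final 4 weeks of Stage 1 accrual. Four immature subjects then correspond to about one per week. The documents give no accrual rate, so k is an assumption and the table is a range.

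**Boundary used.** Power and alpha use the Table 8 final boundary (12 or more of 67). The text of Section 9.1 requires 15 or more, which gives alpha 0.005 and power 0.573 even with k = 0. That mismatch is a separate matter. The false-stop column does not depend on it.

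**The case against.** The strongest reply is that the documents never say a pending response is a non-response. Section 9.1 only speaks of subjects who respond, and a sponsor could count such a response or wait for it. Eight weeks is also the lower end of an exposure window reaching 8 cycles, not a look date, and the plan plainly expects Stage 1 data to mature. This stands. A reader might infer that late-enrolled responders will be counted as non-responders, but the documents support only that they may be. The gap remains: nothing requires a later look, and counting unconfirmed responses would make the Stage 1 endpoint differ from the final one.

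A reader might also infer that a subject at the minimum cannot be a responder at all. That goes too far. The condition is time on treatment, not follow-up. Section 6.4 allows interruptions of up to 28 days, Section 7.2 continues tumor assessment after treatment stops for reasons other than progression, and Section 8.6 permits unscheduled evaluation. The 12-week limit holds for continuous dosing on scheduled scans.

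The size is open to challenge too. Notch alterations are reported in only 5 to 16% of TNBC (Section 2.1), so accrual may be slow and k small. That is fair, and the range therefore starts at 0.

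Finally, Section 9.4 leaves detail to the SAP. But Section 9.3 requires the SAP only before database lock, so it need not exist when the futility decision is taken.

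**Conclusion.** The point holds as a gap in the stated rule. The 8-week minimum in Section 9.4 is about 4 weeks shorter than the endpoint needs on scheduled scans, and no text protects a response awaiting confirmation. Applied literally at the minimum, the rule can stop an active drug more often than the 12.0% built into the design.

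The loss is modest if few subjects are immature: with one, 14.0% false stopping and power 0.791; with two, 16.4% and 0.773. It is substantial with six: 29.2% and 0.666. These figures assume a true ORR of 23%, the Table 8 boundaries, and no immature response visible at the look. They are conditional on k and do not predict what will happen. If the sponsor waits for the data to mature, k is 0 and Table 8 stands. Type I error does not rise, so the harm is confined to loss of power.

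**What to change.** Amend Section 9.4 to say that the 4-of-26 rule uses confirmed responses, and that futility is declared only when each of the 26 evaluable Stage 1 subjects meets one of these conditions:

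- has a confirmed response;
- has progressed, died, started new anticancer therapy, withdrawn, been lost to follow-up or otherwise ended tumor assessment;
- has been followed for at least about 12 weeks from first dose, with any pending PR or CR resolved by its confirmation scan.

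Stage 1 is positive as soon as 4 confirmed responses are reached. The second condition must cover subjects who withdraw or are lost; otherwise one such subject could block the decision indefinitely. Twelve weeks covers responses first seen at the first scan. If later first responses are meant to count at Stage 1, the sponsor should state a longer follow-up.

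The cost is a short text change and a futility read at least about 4 weeks later than the stated minimum. Stage 2 enrolment already continues in that time under Sections 9.1 and 9.4, so accrual is not delayed, but a few more subjects may be enrolled before a true futility stop.
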